## 1.0 Objectives / Specific Aims

The overarching hypothesis is that endoscopic treatment of main pancreatic duct obstruction due to chronic pancreatitis reduces pain and improves quality of life. There is a critical need to test this hypothesis, since ERCP is often performed in clinical practice despite limited data and potential negative short- and long-term consequences on the natural history of chronic pancreatitis.

### 1.1. Aim #1. To determine the feasibility of a sham-controlled pancreatic endotherapy trial.

The *PERCePT* study is a pilot, sham-controlled, randomized clinical trial to evaluate the feasibility of recruitment, retention, and blinding procedures, as well as to refine the enrollment criteria for a subsequent definitive clinical trial. Patients with painful chronic pancreatitis and main pancreatic duct obstruction will be randomized to endoscopic ultrasound (EUS) + sham versus EUS + ERCP with pancreatic endotherapy, the latter being defined by the use of extracorporeal or intraductal lithotripsy, stone extraction, stricture dilation, stent placement, or some combination. Pancreatic duct obstruction will be defined by the presence of a main pancreatic duct stone, stricture, or both, with consequential upstream dilation of the main pancreatic duct  $\geq 6\text{mm}$ . After completion of the initial endoscopic intervention, patients will be assessed by individuals blinded to treatment allocation for 90 days. At this time, subjects will complete a comprehensive assessment including measures of pain, quality of life, sleep, mood, functioning, and medication use. All subjects will continue to be followed for 12 months after the randomization procedure to assess longer term outcomes.

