## 2.6 Quality of life is significantly reduced among patients with chronic pancreatitis, primarily due to pain

Patients with chronic pancreatitis have lower quality of life, as quantified by significantly lower physical and mental component scores compared to healthy controls and even patients with acute recurrent pancreatitis. The presence of constant abdominal pain and disability due to chronic pancreatitis-related symptoms are two of the most important factors associated with lower quality of life. Reductions in opioid utilization following total pancreatectomy are closely associated with improvements in physical and mental components of quality of life. Since interventions to improve pain would be expected to improve quality of life and disability, the primary outcome for this pilot study will focus on pain. Recognizing the complex interaction between pain, depression, quality of life, catastrophizing, and opioid misuse, among others, a secondary aim of this pilot study is to examine several potential outcome measures in anticipation of a definitive clinical trial to follow.

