## **4.0 Study Endpoints**

### **4.1 Pilot primary outcome**

The primary efficacy outcome for this pilot study will be average daily pain from the electronic diaries during the 14-day period preceding the 90-day assessment, compared to the average daily pain reported during the 14-day run-in. Clinical improvement will be defined by the change in the average pain score between these two intervals, and without the need for increased opioids or additional interventions/procedures. A standardized 11-point Numeric Rating Scale (NRS) will be used to capture average daily pain with the empirically-supported anchors of 0=No Pain and 10=Worst Pain Imaginable.

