### **4.2 Pilot secondary outcomes**

At 90-days, change from baseline in functional impairment due to pain (BPI), quality of life, opioid misuse, pain catastrophizing, depression, and central sensitization will be examined.

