## 10.0 Study Design / Methods

### 10.1 Study procedures

#### 10.1.1 Run-in period

A schedule of study procedures is detailed in **Table 1**. To summarize, potential subjects will be identified in GI medicine and surgery clinics where they will be screened for eligibility. If eligible and the subject completes the informed consent process, a 14-day run-in period

will commence. During this time, the subject will complete a daily diary using an Ecological Momentary Assessment tool developed for this pilot study. The diary will include the 11-point Numeric Rating Scale for pain, number of hours of sleep the night prior, activity level (11-point scale), and details on opioid medication use in the past 24 hours. In addition, the subject will undergo Quantitative Sensory Testing (QST).

**Baseline Assessment.** Once consent is obtained, eligible subjects will be enrolled and complete a baseline assessment, which will include several validated instruments measuring pain, pain quality, quality of life, psychological factors and comorbidities, sleep, opioid use, alcohol use, and pain-related disability (**Table 2**). Additionally, patients will undergo QST to assess thermal pain thresholds, tolerance and central sensitization via wind-up and conditioned pain modulation tasks. The baseline assessment is estimated to include an approximately 1-hour visit to complete the baseline measures and a separate 1-hour visit for the QST in the Behavioral Medicine laboratory.

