**Ecological Momentary Assessment (EMA).** Given the variability in pain patterns and potential for recall bias, all eligible patients will complete a 14-day run-in period where pain, psychological status, and use of analgesics will be measured prospectively. Ecological Momentary Assessment (EMA) will be employed via Electronic Daily Diaries administered by phone, SMS or using survey links sent to the patient's cellphone or e-mail address. If a subject does not have access to a smartphone, they may be provided with a smartphone for the duration of the study (up through the 90-day follow-up assessment). We will assess daily (via standard 11-point numeric rating scales (0-10); NRS) average pain, pain at its worst, pain unpleasantness, mood, anxiety, activity level, opioid cravings, and will assess amount of prescription opioid and other substance use. We have developed a SMS/MMS encrypted gateway which enables ecological momentary assessment of these variables. This communication system was selected due to its widespread availability on all major cell phone types and their carriers. Measures will be collected at random times during waking hours each day to minimize response bias associated with event related reporting.

Medical management during the run-in period will include dose adjusting analgesic medication, if necessary. During the run-in period and prior to randomization, it is possible that subjects will improve clinically which that endotherapy is no longer appropriate. The decision to proceed with endotherapy will be based on usual clinical care, but primarily related to the persistence of abdominal pain with an average daily pain score  $\geq 4$  as per study enrollment criteria. However, we are reluctant to have additional pre-specified criteria since

the decision to proceed with procedural intervention is nuanced. These subjects will continue to be followed systematically as an observational cohort but not undergo the randomization procedures. If the subject continues to meet enrollment criteria after the 14-day run in period, the subject will proceed to the randomization procedures. The observational cohort will be capped at n=15 and will follow the same data collection schedule as the randomized cohort.

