The DCU's risk-based monitoring approach is based upon the premise that a certain level of random error in non-critical data is acceptable and that efforts should be focused on decreasing errors in data associated with the planned analysis and human subject protection. The level of risk is affected by factors including study design, study endpoints, study population, experience of investigators, data collection methods, safety profile of an investigational product/intervention, stage of the study, and quantity of data. Prior to the start of the study, the study team will identify the risks associated with the trial. This monitoring plan is then developed to most effectively mitigate these critical risks, if the source of risk cannot be eliminated entirely.

**11.2 Sample Size.** A total of 30 subjects will be randomized (15 per arm) within a 21-month period. In a recent retrospective cohort study including patients undergoing first-time pancreatic endotherapy for chronic pancreatitis at the Medical University of South Carolina, the average number of new patients/year undergoing pancreatic endotherapy was 22, and > 30 in recent years. This is above our estimated enrollment rate for this pilot study.

**11.3 Data Management.** Paper files will be stored in locked filing cabinets in restricted access offices at OHSU and MUSC. All clinical data on enrolled subjects will be data entered by study personnel into a web-based clinical trials management system, WebDCU, which is managed by the Data Coordination Unit (DCU), Department of Public Health Sciences at MUSC. This user friendly, secure web-based database system, developed by the DCU, will be used for subject randomization, data entry, data validation, project progress monitoring, subject tracking, user customizable report generation and secure data transfer. Access to data will be restricted to study personnel. All study team members will receive a unique user account and ability to set up their own private password. The system has an audit trail to track all logins and enter/edit of study data.

De-identified data from the study will be stored indefinitely. In the event of a screen failure of a consented subject, data collected during screening will be retained for separate analysis.

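### Aim 1 is feasibility, but the plan has no feasibility outcome, no progression value and no measure of blinding; these should be added beside the pain outcome

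*Combined protocol and SAP*

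**What the plan says.** Section 1.1 (Aim 1) sets out "a pilot, sham-controlled, randomized clinical trial to evaluate the feasibility of recruitment, retention, and blinding procedures", and adds refinement of the enrollment criteria for a later definitive trial.

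Section 4.1 then states: "The primary efficacy outcome for this pilot study will be average daily pain from the electronic diaries". Section 2.6 agrees that "the primary outcome for this pilot study will focus on pain", and Section 10.1.3 ties the primary analysis to the pain change score. In Section 4.2 the secondary outcomes are 90-day measures: "change from baseline in functional impairment due to pain (BPI), quality of life, opioid misuse, pain catastrophizing, depression, and central sensitization will be examined". Section 11.4 specifies intention-to-treat analysis, exploratory and descriptive work, and confidence intervals for the secondary outcomes.

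On accrual, Section 11.2 says "A total of 30 subjects will be randomized (15 per arm) within a 21-month period". It gives an MUSC count of new patients having first-time endotherapy for chronic pancreatitis (22 a year on average, more than 30 recently) and concludes: "This is above our estimated enrollment rate for this pilot study". Section 6.0 splits the 30 subjects into about 20 at MUSC and 10 at OHSU.

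**The concern.** The main aim and the endpoint section do not meet. Recruitment, retention and blinding are the three things the pilot sets out to test, and none is defined as an outcome, given a target or assigned an analysis. Without a value fixed beforehand, almost any result can be called feasible. Meanwhile the only outcome labelled primary is a pain comparison from 15 per arm with no stated power basis, and an imprecise estimate may be read as the trial's result. Section 15.1 already discusses benefit by arm, or refutation of the hypothesis.

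Blinding is the most serious gap. Screening and visit records can be counted later, but a subject's belief about allocation cannot be recovered once the allocation is known. Table 1 and Section 10.1.3 allow unmasking and open-label procedures from day 90. The definitive sham-controlled trial would then be planned without evidence that the sham works.

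**Working it through.** **1. Aim set against outcome.**

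- Recruitment: Section 11.2 gives 30 in 21 months as the plan, not as a success criterion. A screening log exists (Section 8.0), but its stated use is demographic tracking.
- Retention: Section 13.0 says missed visits are documented. There is no definition of retained and no target.
- Blinding: Section 10.1.2 prescribes a stay of at least 45 minutes in the suite after randomization. That is a procedure, not a measurement. Table 2 has a pre-procedure expectation item and Table 3 a global impression of change; neither asks which treatment the subject thinks was given. Table 1 has no such item for subjects or assessors.

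**2. The plan's own figures.** 15 + 15 = 30 and 20 + 10 = 30, so the totals agree. Planned rates are:

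- Overall: 30/21 = 1.43 per month, or 30/21 × 12 = 17.1 per year.
- MUSC: 20/21 × 12 = 11.4 per year.
- OHSU: 10/21 × 12 = 5.7 per year.

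The statement that 22 a year is above the planned rate is therefore correct.

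**3. Share of the MUSC pool required.** Required share = 20 / (annual count × 21/12).

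- At 22 a year: pool 38.5, share 20/38.5 = 52%.
- At 30 a year: pool 52.5, share 20/52.5 = 38%.

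The count already reflects chronic pancreatitis and no previous endotherapy. It is not stated to be filtered for duct dilation ≥ 6 mm, run-in pain ≥ 4 or consent to a sham. No conversion rate is given. If 30% of the pool were randomized (assumed), 20 subjects would take 20/(22 × 0.30/12) = 36 months, or 27 months at 30 a year. At 50% (assumed) it would take 22 or 16 months.

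**4. Precision of the pain difference.** Half-width = t(0.975, 28) × SD × √(2/15) = 2.048 × SD × 0.365. The documents give no SD of change, so the SDs are assumed:

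| SD of change | 95% CI half-width (NRS points) |
|---|---|
| 1.5 | 1.1 |
| 2.0 | 1.5 |
| 2.5 | 1.9 |
| 3.0 | 2.2 |

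**5. What 30 subjects can say about retention.** Exact (Clopper-Pearson) 95% intervals: 27/30 = 90% (73 to 98%); 24/30 = 80% (61 to 92%). Exact binomial probability of a go, with illustrative thresholds:

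| Go rule | True retention 70% | True retention 90% |
|---|---|---|
| ≥ 24/30 | 16% | 97% |
| ≥ 26/30 | 3% | 82% |

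A usable rule exists at this sample size, and its properties depend strongly on the cut-off.

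**6. Blinding.** If 8 of 15 in an arm guessed correctly, the estimate would be 53% (exact 95% CI 27 to 79%). That is coarse, but it would detect gross failure.

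**The case against.** Several points on the other side stand. Section 4.1 says primary efficacy outcome, which leaves room for a separate feasibility outcome. Pain data also serve Aim 2 directly. Section 11.4 provides for descriptive statistics, so accrual and retention could still be reported. It would be too strong to say that the pilot can learn nothing about feasibility. What these points do not supply is a definition, a threshold or a blinding measure.

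A reader might infer that the recruitment support is an unfiltered procedure count. It is not: Section 11.2 counts new patients, already limited to first-time endotherapy for chronic pancreatitis, which matches the exclusion for previous endotherapy.

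A reader might also note that in Section 10.1.1 "Once consent is obtained, eligible subjects will be enrolled and complete a baseline assessment" and "The observational cohort will be capped at n=15", add 30 + 15 = 45, and set 45/21 × 12 = 25.7 per year against 22. The documents do not support that comparison. It puts a two-site requirement against a one-site count, and 15 is a cap, not an expected number. The observational subjects are those who do not go on to the randomization procedures, whereas the 22 are patients who had endotherapy. Section 6.0 also uses enroll for the same 30 who are randomized.

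Finally, the recruitment count does not cause the main problem. It bears only on how plausible 30 in 21 months is.

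**Conclusion.** The point holds in this form. The plan states a feasibility aim but gives no feasibility outcome, analysis or progression value. Recruitment and retention can be described but not judged by a pre-set rule. Blinding cannot be assessed, because nothing scheduled measures it and the information is lost at unmasking. The accrual sentence is true, with a narrower margin than it suggests: MUSC must randomize 38 to 52% of its counted pool before losses that the plan does not quantify, and OHSU's 10 subjects have no supporting count.

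The pain half-width of 1.1 to 2.2 points rests on an assumed SD of change of 1.5 to 3.0. The retention thresholds and conversion rates are also illustrations, not document values. The absence of feasibility outcomes and of a blinding measure rests on the text alone. This should be corrected; it does not call for a change to sample size, arms or treatment.

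**What to change.** In Section 4, keep diary pain as the primary efficacy outcome, reported as an estimate with a confidence interval only, and add feasibility primary outcomes beside it:

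1. **Recruitment:** subjects randomized per month against the plan's 1.43, with counts screened, eligible, consented and randomized. Confirm that the screening log captures each of these.
2. **Retention:** the proportion of randomized subjects with primary-outcome diary data. Subjects re-intervened before day 90 count as having data when the pre-intervention diary described in Section 10.1.3 is available. The sponsor should set go and amend values now, with the error rates of the chosen cut-off shown as in the table above.
3. **Blinding:** a treatment-guess question to subjects and blinded assessors, asked before any unmasking and at the latest at the start of the day-90 visit, reported by arm. Add it to Tables 1 and 3.

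In Section 11.4, specify exact 95% confidence intervals for these outcomes. In Section 11.2, keep the sentence that 22 a year exceeds the planned 17.1. Add the 52% and 38% shares, the criteria for which the count is not stated to be filtered, and the absence of an OHSU count.

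The cost is one added form item, a commitment to thresholds and a less favourable recruitment statement.

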### 1.2. Aim #2. To define the optimal outcomes for a definitive clinical trial.

The goals of pancreatic endotherapy are to reduce pain, improve pancreatic function, and thus improve quality of life and other patient-centered outcomes. The optimal outcome measures for a definitive clinical trial will be defined. Pain, pain-related disability, patient expectation of response, and quality of life will be measured at baseline, 90 days, 6 months, and 12 months following the randomization procedure. Changes in pain and disability and the relationship to quality of life and patient expectation (the nocebo effect) will be evaluated. An essential component to defining outcomes related to pain is to identify what is important to the patient. The baseline case report forms and follow-up assessments will include querying subjects to prioritize outcomes of pancreatic endotherapy.

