### 10.1.2 Baseline and randomization procedures

The subject will complete baseline instruments detailed in **table 2**. The subject will return on study day 0. Patients will be compensated \$75 for their time completing the baseline assessments. Women of childbearing potential will be administered a urine pregnancy test. If the result is positive for pregnancy, the patient will be excluded from the study. After confirmation of meeting eligibility criteria, the subject will undergo the randomization procedures (endoscopic ultrasound + sham pancreatic endotherapy or endoscopic ultrasound + ERCP with pancreatic endotherapy).

All subjects will undergo anesthesia administered sedation and endoscopic ultrasound (EUS). The endoscopist will assess the pancreas for parenchymal and ductal features of chronic pancreatitis and confirm the absence of exclusion criteria (such as the presence of an occult pancreatobiliary malignancy). Following the completion of the EUS, assuming that eligibility criteria are still met, and while the subject remains under anesthesia, the subject will be randomized to ERCP with pancreatic endotherapy or EUS only (sham). If randomized to sham, the endoscopist will not perform ERCP. To maintain the blind, the patient and clinical team will stay in the endoscopic suite for at least 45 minutes after randomization. This is the average length of time the ERCP with endotherapy could take if randomized to this group.

If randomized to ERCP with pancreatic endotherapy, the endoscopist will proceed with this intervention immediately following the completion of EUS and treatment allocation (during the same anesthesia). Pancreatic endotherapy may include any or all of the following maneuvers: pancreatic endoscopic sphincterotomy, stricture dilation using a bougie or hydrostatic balloon catheter, pancreatic stone extraction with or without mechanical or electrohydraulic lithotripsy, extracorporeal shock wave lithotripsy, and stent placement. Overall technical success will be defined by the ability to insert at least one pancreatic stent across the dominant main pancreatic duct obstruction. Technical success for pancreatic stone treatment will be defined by the ability to remove all fluoroscopically visible main pancreatic duct stones.

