The day 90 follow-up assessment will include completion of selected instruments and a discussion with blinded physician investigators about their clinical course. It is not realistic to assign a threshold pain score above which further intervention should be offered, so it is expected that the blinded physicians and patient will decide whether an intervention is required to treat pain; this highlights the importance of the study's sham design. Potential scenarios are detailed in *figure 2*. Although not incorporated into this study's pilot primary outcome, it is expected that a decision to proceed with an intervention to treat pain would be considered a "failure" of pancreatic endotherapy in a definitive clinical trial. Each of the groups in figure 2 are explained in further detail below. The design of the hierarchical diagram is deliberate and intends to illustrate that management options for groups 3 and 4 are the same. In addition, follow-up is in part dependent on the original treatment allocation. So, after all blinded assessments have been completed and a decision regarding intervention determined, an unblinded investigator will need to advise the subject regarding next steps. Participants will be compensated \$75 after completing the 90-day follow up visit. If participants complete all visits, they will be compensated a total of \$200.

**1. Sham group, no intervention advised.** In this scenario, the subject is doing well enough that no intervention is advised. Since no procedures have been performed until this point, continued medical management is reasonable. The subject would be followed through day 360 for relevant changes in clinical course and to assess secondary endpoints.

[figure not shown]
**2. Endotherapy group, no intervention advised.** In this scenario, the subject is doing well enough that no intervention is advised. Since pancreatic endotherapy had been performed during the randomization procedure, the subject would be advised to undergo repeat pancreatic endotherapy to remove pancreatic duct stents. In some cases, the treating endoscopist may recommend replacing or upsizing stents in an effort to minimize stricture recurrence. This will be determined by the unblinded treating physician per standard of care. Follow-up procedures would be open-label, although it is possible that the subject remain blinded to their original treatment allocation.

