**Figure 2. Potential scenarios during the 90-day follow-up visit**

#### 10.1.4 Follow-up visits, day 91-360

Every effort will be made to preserve the integrity of the original treatment allocation, recognizing the need for a pragmatic approach to the follow up period. Although 90-day outcomes will be the focus of this pilot study, all subjects will be followed for 12 months after randomization at which point the same outcome measures will be assessed. These data will be used to examine changes in the 90-day and 12-month outcomes, recognizing that interventions performed after 90 days will be unblinded.

The content of follow-up visits at days 180, 270, and 360 are detailed in **table 3** and may be completed by telephone or in-person.

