Opioid Utilization	Current Opioid Misuse Measure (COMM)	X	X	X	X	
 
• Self-report measures of risk for aberrant medication-related behavior in patients prescribed opioids for chronic pain
 
• 3-minutes
 

Pain Catastrophizing	Pain Catastrophizing Scale (PCS)	X	X	X	X	
 
• Measurement of negative cognitive-set brought to bear during painful experiences
 
• Predictor of functional impairment due to pain and pain-related depression
 
• 5-minutes
 

Patient Global Impression of Change	PGIC	X	X	X	X	
 
• Patient's assessment of efficacy from the index ERCP procedure
 
• 1 minute
 

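### Aim 1 sets out to evaluate blinding procedures, but the protocol specifies no measure of perceived allocation, no record or report of unmaskings, and no blinding outcome or analysis

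*Combined protocol and SAP*

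**What the plan says.** Section 1.1 names three feasibility targets: the pilot is to "evaluate the feasibility of recruitment, retention, and blinding procedures".

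The protocol gives several steps for keeping the blind. Subjects are randomized under anesthesia, and section 10.1.2 adds that "the patient and clinical team will stay in the endoscopic suite for at least 45 minutes after randomization". Blinded physicians manage and assess subjects up to day 90 (section 10.1.3, Table 3). Section 14.6 provides an urgent route for unmasking a treating provider through the coordination center.

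Two planned instruments come close to the subject. Section 1.2 says that "patient expectation of response, and quality of life will be measured at baseline, 90 days, 6 months, and 12 months", and Table 2 describes expectation as how far the patient expects to improve. Table 3 lists the PGIC as the patient's "assessment of efficacy from the index ERCP procedure".

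On day 90, section 10.1.3 states that "after all blinded assessments have been completed and a decision regarding intervention determined, an unblinded investigator will need to advise the subject". For endotherapy subjects who are doing well, "the subject would be advised to undergo repeat pancreatic endotherapy to remove pancreatic duct stents". Sham subjects who are doing well continue medical management.

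Sections 4.1 and 4.2 list pain and other patient-reported or sensory outcomes. Section 11.4 gives the ITT principle and refers generally to exploratory and descriptive analyses. Neither section mentions blinding.

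**The concern.** Of the three targets in Aim 1, blinding is the only one without a named data source. Recruitment has a screening log (section 8.0) and a goal of 30 subjects in 21 months (section 11.2). Retention has documented withdrawal dates and reasons, and documented missed visits (section 13.0). For blinding there are procedures but no measure of whether they worked.

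Whether they work is an open question on the protocol's own figures. Section 14.8 puts post-ERCP pancreatitis at 5-10%. Section 2.4 puts short-term adverse events of endotherapy, including worse pain, at up to 40%. Such events could hint at allocation. The 45-minute minimum is tied to an average duration, so actual ERCP times may differ from it.

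The blind bears on the primary outcome in two ways. Pain is self-reported (section 4.1). A blinded physician also decides on re-intervention before day 90, and that decision changes which pain data enter the change score (section 10.1.3). A definitive sham-controlled trial would want to know from this pilot whether the blind held.

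**Working it through.** The plan states no figure on this point, so there is none to reproduce. The check has two parts.

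**1. Where a blinding measure could appear**

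- Sections 4.1 and 4.2 (endpoints): none.
- Table 1 (schedule): none. It foresees unmasking at day 90 for some sham subjects but gives no record or count.
- Table 2 (baseline): expectation of improvement, which is not belief about allocation.
- Table 3 (follow-up): PGIC, which rates efficacy and does not ask which procedure was done. No item on perceived allocation is listed with the blinded physician evaluation.
- Section 11.3: the audit trail covers logins and data entry or edits. It does not say that unmaskings are logged.
- Section 14.6: covers urgent unmasking of a treating provider. It says nothing on recording reasons, on subjects, or on accidental unmasking of a blinded assessor.
- Section 11.4: no blinding analysis.

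**2. What an added item could show**

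Input: 15 per arm (section 11.2; 15 × 2 = 30, which agrees with 10 + 20 in section 6.0). All answer splits below are assumptions.

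Bang index per arm = (correct − wrong)/N. Variance = [pc + pw − (pc − pw)²]/N, where pc and pw are the proportions correct and wrong. The 95% half-width is 1.96 × √variance.

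| N | Correct / wrong / unsure | Index | 95% CI | Half-width |
|---|---|---|---|---|
| 15 | 5 / 5 / 5 | 0.00 | −0.41 to 0.41 | 0.41 |
| 15 | 7 / 3 / 5 | 0.27 | −0.12 to 0.66 | 0.39 |
| 15 | 8 / 2 / 5 | 0.40 | 0.04 to 0.76 | 0.36 |
| 15 | even split, none unsure | 0 | −0.51 to 0.51 | 0.51 |
| 12 | 4 / 4 / 4 | 0.00 | −0.46 to 0.46 | 0.46 |
| 12 | even split, none unsure | 0 | −0.57 to 0.57 | 0.57 |

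Example, first row: √[(1/3 + 1/3 − 0)/15] = 0.211, and 1.96 × 0.211 = 0.41. With 5 of 15 unsure, 0.40 is the smallest index whose lower limit exceeds zero.

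The arms must be read together. Suppose that in each arm 10 of 15 believe they had ERCP, 2 believe sham and 3 are unsure. The index is then +0.53 (0.17 to 0.90) with ERCP and −0.53 (−0.90 to −0.17) with sham. The difference between arms in believing ERCP is 10/15 − 10/15 = 0, with half-width 1.96 × √[2 × (2/3)(1/3)/15] = 0.34. The pattern is compatible with optimism shared by both arms but does not exclude partial unblinding.

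For zero unmaskings, the exact two-sided 95% upper limit is 1 − 0.025^(1/15) = 22% per arm and 1 − 0.025^(1/30) = 12% overall. These limits apply to all unmasking only if every kind of unmasking is recorded.

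**The case against.** The strongest reply is that Aim 1 speaks of blinding procedures, and feasibility can be read operationally: were the 45-minute stay and the blinded assessments delivered? These could be described under the general wording of section 11.4. That stands in part, although the protocol does not commit to it. It would still leave open whether anyone remained blind.

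Second, absence from the tables is weaker evidence here than usual. Section 1.2 promises follow-up expectation and outcome-priority questions that Table 3 does not list, and Table 3 refers to case report forms that are not among the documents. An item could exist there. This limits the claim to what the protocol specifies. An unseen item would still need an outcome and an analysis.

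Third, a reader might infer that the information can be gathered later. Section 10.1.3 says of follow-up procedures after endotherapy, "although it is possible that the subject remain blinded to their original treatment allocation", and section 10.1.4 says "Every effort will be made to preserve the integrity of the original treatment allocation". The first is only a possibility. The second concerns allocation, not the blind, and the same section says that interventions after 90 days are unblinded. Because care then differs by arm even for subjects doing well, later answers would not be on equal terms.

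Fourth, the yield is modest: the sample is small, and day 90 beliefs are confounded by perceived improvement. Both points stand. They argue for a short, descriptive measure rather than for none.

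**Conclusion.** The omission is real and should be fixed; confidence is medium because the case report forms cannot be seen. If the protocol is followed as written, the masking steps could be described. Whether subjects and blinded physicians remained blind could not be, and that cannot be recovered after day 90.

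Several stronger readings are tempting, and the documents do not support them. A reader might infer that the blind is inadequate or will fail; nothing shows this, and section 14.6 states the intent to limit unmasking. A reader might infer that unmasking is not provided for; a route exists, and only its recording and reporting are unspecified. A reader might infer that the primary comparison is invalid; the gap does not affect safety, the definition of the pain outcome or the ITT analysis.

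On size, a per-arm Bang index with 15 answers would carry a 95% half-width of about 0.36 to 0.51 over the assumed splits (0.46 to 0.57 in the two cases with 12 answers). Only gross failure of the blind would show.

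**What to change.** - **Belief item.** At the existing day 90 visit, after the patient-reported measures and before the treatment discussion or any unmasking, ask subjects and the blinded physicians which procedure they think was done (ERCP, sham, does not know) and the main reason. Ask the subject and the deciding physician the same before any earlier re-intervention.
- **Unmasking form.** Record every unmasking of a subject, treating provider or blinded assessor before the day 90 assessments are complete, with date, person and reason. Sections 11.3 and 14.6 do not establish such a record.
- **Section 4.** List both as Aim 1 outcomes.
- **Section 11.4.** Report beliefs and unmaskings by arm with 95% CIs, descriptively and without a pass/fail test. State that day 90 beliefs are confounded by perceived improvement. A per-arm Bang index is optional; if used, read the arms together.
- **Optional early item.** A question at the day 7 or day 30 call is less confounded by perceived improvement, but it may prompt speculation before the day 76-90 diary. This is a trade-off for the investigators.

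Cost: up to 30 subject answers and 30 × 2 = 60 physician answers at day 90, a few more for early re-interventions, one small form, and an amendment to the protocol and case report forms. The optional early item adds up to 30 answers.
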